6.8. Subgroup analysis

No subgroup analysis is planned

6.9. Safety data analysis

Reporting of safety information will be split into subsets by first phase, second phase, third phase, and fourth phase.

Adverse Events: Summary tables for adverse events (AEs) have to include only AEs that started or worsened during the on-treatment period, the treatment-emergent AEs (TEAEs). However, all safety data (including those from the pre-treatment period) will be listed and those collected during the pre-treatment period are to be flagged.

The incidence of treatment-emergent adverse events (new or worsening from baseline) will be summarized by system organ class and/or preferred term, severity (based on CTCAE grades), type of adverse event, causality relation to study treatment by the phases or subsets previously described.

Deaths reportable as SAEs and non-fatal serious adverse events will be listed by patient and tabulated by type of adverse event and safety subset.

Specific safety event categories will be considered. Such categories consist of one or more well-defined safety events which are similar in nature and for which there is a specific clinical interest in connection with the study treatment(s).

For each specified safety event category, number, and percentage of patients with at least one event part of the safety set will be reported. Also, AESI will be summarized and analyzed.

Laboratory abnormalities: For laboratory tests covered by the Common Terminology Criteria for Adverse Events (CTCAE) version 5.0 the study's biostatistician and reporting team will grade laboratory data accordingly. For laboratory tests covered by CTCAE, a Grade 0 will be assigned to all non-missing values not graded as 1 or higher. Grade 5 will not be used.

In some cases, (e.g., white blood cell differentials) the lower limits of normal ranges used in CTCAE definition have to be replaced by a clinically meaningful limit expressed in absolute counts.

For laboratory tests where grades are not defined by CTCAE, results will be graded by the low/normal/high classifications based on laboratory normal ranges.

The following by-safety subset summaries will be generated separately for hematology, and biochemistry tests:

- number and percentage of patients with clinically significant laboratory abnormalities, by parameter and worst post-baseline CTCAE grade. Each patient will be counted only for the worst grade observed post-baseline, regardless of the baseline status
- shift tables using CTCAE grades to compare baseline to the worst on-treatment value
- for laboratory tests where CTCAE grades are not defined, shift tables using the low/normal/high
- classification to compare baseline to the worst on-treatment value.
- listing of all laboratory data with values flagged to show the corresponding CTCAE grades and the classifications relative to the laboratory normal ranges.

Other Safety Data: other safety data collected (e.g., ECG, vital signs) will be listed and summarized using descriptive statistics as appropriate. Notable values will be flagged. Notable/Abnormal values for safety data will be further specified in the RAP.

The list of safety data will be summarized as:

Variables	Data
Laboratory (hematology, biochemistry, urinary and others), Vital signs, changes in physical exam findings and Electrocardiogram abnormalities	Number and percentage Description (mapped to MedDRA thesaurus terms) Time of appearance in relation to study's drug administration/data of onset (n-TEAE or TEAE, days/hours) End date or ongoing until recovery or stability Severity-CTCAE grades (from 0 to 5 or low/normal/high for laboratory tests or according to study protocol) Seriousness (according to definitions of study protocol) SAE (yes or not) Causality (Definitely Not Related, Probably Not Related, Possibly Related, Probably Related or Definitely Related) Expectedness (according to Clinical Investigator's Brochure) Outcome/evolution Any medication used to treat the AE or concomitant medication (yes or not, an specify active substance name, dose, and frequency) If it requires further exams/test(yes or not, an specify)
Hypersensitivity	
Adverse Event of Special Interests (AESI): 1. Myocardial infarction 2. Angina 3. Coronary artery disease 4. Cerebrovascular ischemic disease 5. New onset or worsening of peripheral artery occlusive disease 6. Retinal vascular thrombosis, both venous and arterial. 7. Venous thromboembolism that could result in significant compromise of organ function or other significant consequences 8. Any other event considered important by the investigator	
Pregnancy	

All variables will be recorded, ongoing or starting within 28 days after end of treatment/patient decision to discontinue treatment (pos-treatment).

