- after prior platinum containing chemotherapy, or
- who are considered cisplatin ineligible, and whose tumours have a PD-L1 expression ≥ 5%.

Also, in combination with bevacizumab, paclitaxel and carboplatin, atezolizumab is indicated for the first-line treatment of adult patients with metastatic non-squamous non small cell lung cancer (NSCLC). In patients with EGFR mutant or ALK-positive NSCLC, atezolizumab, in

combination with bevacizumab, paclitaxel and carboplatin, is indicated only after failure of appropriate targeted therapies.

Atezolizumab as monotherapy is indicated for the treatment of adult patients with locally advanced or metastatic NSCLC after prior chemotherapy. Patients with EGFR mutant or ALK positive NSCLC should also have received targeted therapy before receiving atezolizumab.

Atezolizumab at a dose of 1–20 mg/kg produced a dose-proportional increase in exposure to the drug. Typical clearance was 0.20 L/day, volume of distribution at steady state was 6.9 L, and the terminal half-life was 27 days, according to a population analysis of patients in the dose range (n = 472). This population analysis also suggested steady state occurs after 6–9 weeks treatment (2–3 dosage cycles). Systemic accumulation in terms of area under the plasma concentration time curve (AUC), maximum concentration (C_{max}) and trough concentration (C_{min}) was 1.91, 1.46 and 2.75-fold, respectively. The systemic exposure to atezolizumab was not significantly affected when analysed according to patient age, body-weight, gender, positive anti-therapeutic antibody status, albumin levels, tumour burden, region or race, mild or moderate renal impairment, mild hepatic impairment, level of PD-L1 expression, or Eastern Cooperative Oncology Group (ECOG) performance status. The potential for atezolizumab to interact with other drugs is unknown (*Markham, 2016; EMA, 2019*).

Major common AEs involved fatigue, decreased appetite, nausea, diarrhea, pyrexia, pruritus, cough, edema peripheral, and rash. The most common severe AEs were fatigue, anemia, and dyspnea. The overall atezolizumab-related death rate was much lower than chemotherapeutics-related death rate. Atezolizumab has better overall survival and lower risk of AEs compared with chemotherapy (*Tie, 2019*).

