9.4 Third Therapy

All patients completing cycle 12 with bosutinib plus atezolizumab therapy will continue with bosutinib 400 mg/day in monotherapy for 12 more cycles.

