11.6.2 Dose reduction steps for atezolizumab

Although most immune-mediated adverse events observed with immunomodulatory agents have been mild and self-limiting, such events should be recognized early and treated promptly to avoid potential major complications. Discontinuation of atezolizumab may not have an immediate therapeutic effect and, in severe cases, immune-mediated toxicities may require acute management with topical corticosteroids, systemic corticosteroids, or other immunosuppressive agents.

The investigator should consider the benefit-risk balance a given subject may be experiencing prior to further administration of atezolizumab. Atezolizumab should be permanently discontinued in subjects with life-threatening, immune-mediated adverse events. Specific guidelines for immune-mediated events are provided in Tables 3 to 13.

For all other non-immune mediated adverse events, including infections, atezolizumab should be withheld for Grade 3 or higher toxicity with the following exceptions:

- Grade 3 nausea that responds to antiemetic treatment within 7 days
- Grade 3 vomiting that responds to antiemetic treatment within 7 days
- Grade 3 diarrhea that responds to antidiarrheal treatment within 7 days
- Grade 3 fatigue that was present at baseline or that lasts for <7 days after the last administration of atezolizumab
- Grade 3 asthenia that was present at baseline or that lasts for <7 days after the last administration of atezolizumab

Administration of atezolizumab may be restarted upon recovery from toxicity to Grade 1 or baseline.

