12 VISIT SCHEDULE AND ASSESSMENTS

12.1 Schedule of Events

Details on scheduling and sample collection are described in Tables 14-17. The tables 14 and 15 for 1st group of patients (first 10 patients included), and the tables 16 and 17 for 2nd group of patients (the last 26 patients included).

All data obtained from these assessments must be recorded in the source documentation. The CRF will not be used as a source document for any study data.

Please maintain a special awareness of the assessments of the primary and secondary endpoints.

All visits should be completed on the designated day or as close as possible. However, the windows allowed by protocol will be:

- For visits that take place every two weeks, the window will be ± 3 days.
- For visits that take place every 4 weeks, the window will be ± 3 days.
- For visits that take place every 3 cycles (every 12 weeks), and the End of Treatment visit, the window allowed will be ± 14 days.

For this purpose, a cycle equal to 28 days (4 weeks) will be defined and one month will be considered to be equivalent to one cycle.

Table 14. Schedule of Assessments 1st and 2nd Therapies for the First 10 Patients

The following visit schedule will apply if the atezolizumab dose does not need to be adjusted during 2nd therapy due to DLTs. If the dose of atezolizumab has to be modified to the 840 mg every two weeks, additional visits will be scheduled for the administration of atezolizumab. The only procedure to be conducted during these additional visits is the administration of atezolizumab

1 st Group of Patients (The 10 First Patients)		1 st Therapy		2 nd Therapy													
VISIT	Visit 0	Visit 1	Visit 2	Visit 3	Visit 4	Visit 5	Visit 6	Visit 7	Visit 8	Visit 9	Visit 10	Visit 11	Visit 12	Visit 13	Visit 14	Visit 15	Visit 16
Cycle	Screening / Baseline	Cycle 1		Cycle 2		Cycle 3		Cycle 4	Cycle 5	Cycle 6	Cycle 7	Cycle 8	Cycle 9	Cycle 10	Cycle 11	Cycle 12	Cycle 13
Day within Cycle (Visit Window ± 3 Days)	-28/-1	1	15	1	15	1	15	1	1	1	1	1	1	1	1	1	1
Consecutive Days in the Study (D)	-28/-1	D1	D15	D29	D43	D57	D71	D85	D113	D141	D169	D197	D225	D253	D281	D309	D337
Informed Consent	X																
Eligibility	X	X ⁽¹⁾															
Inclusion/Exclusion Criteria (Checklist)	X	X ⁽¹⁾															
Medical/Surgical History and Demographics	X																
Recent Medication Prior to First Dose of IMP	X	X ⁽¹⁾															
Leukemia Diagnosis and Prior Cancer Therapy	X																
Sokal Risk Score	X																

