15.3.1 Analysis Set and Grouping for the Analyses

The safety set population will be used for all safety analyses. Reporting of safety information for these patients will be split into subsets by first phase, second phase, third phase, and fourth phase.

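### The phase-split AE tables open a new subset at D365, described as bosutinib monotherapy, with no carry-over rule, while atezolizumab is still at an ordinary pre-dose trough

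*SAP*

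**What the plan says.** The primary objective is the safety profile of the combination (Protocol 8.1; SAP 6.4). SAP 6.5 gives AE frequencies and percentages, with exact binomial intervals, by study phase. SAP 6.9 sets the grouping: "Reporting of safety information will be split into subsets by first phase, second phase, third phase, and fourth phase". Protocol 15.3.1 has the same rule: "Reporting of safety information for these patients will be split into subsets by first phase, second phase, third phase, and fourth phase". The summary tables take AEs with onset or worsening on treatment. Causality is tabulated against study treatment as a whole, not drug by drug, and again within phase.

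After cycle 12 of the combination (study cycle 13), Protocol 9.4 says that patients "will continue with bosutinib 400 mg/day in monotherapy for 12 more cycles".

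On atezolizumab kinetics, Protocol 6.3 states that "the terminal half-life was 27 days".

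Neither document defines a carry-over window, a table by time since last infusion, or an explicit rule for allocating an AE to a phase.

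**The concern.** A calendar split treats the end of infusions as the end of exposure. For a drug with a half-life of about four weeks, dosed every four weeks, it is not. An event on the last day of any combination cycle and an event on D365 occur at about the same atezolizumab level, yet the first is counted under the combination and the second under the later phase.

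The trial has no concurrent control. The periods on bosutinib alone are therefore the only within-trial context for the combination's AE profile. The lead-in lasts one cycle and the post-combination period twelve, so the longer of the two reference periods is the one that starts with residual atezolizumab.

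**Working it through.** **1. Schedule (reproduces the plan's figures).** Protocol 12.1 says "a cycle equal to 28 days (4 weeks) will be defined". Day 1 of cycle c is 1 + 28(c - 1).
- Last every-4-weeks infusion, cycle 13 day 1 (Protocol 11.2.2; Tables 14 and 16): 1 + 28 x 12 = D337.
- Start of third therapy, cycle 14 day 1 (Tables 15 and 17): 1 + 28 x 13 = D365.
- Gap: 28 days. Both days match the tables.

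**2. Level at D365 as a share of the level just after the D337 infusion.** With first-order decay, share = 2^(-t / half-life). The stated half-life gives 2^(-28/27) = 0.487, or 49%.

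**3. Sensitivity.** The other inputs are also from Protocol 6.3: "Typical clearance was 0.20 L/day", a steady-state volume of 6.9 L, and accumulation in AUC, Cmax and Cmin that "was 1.91, 1.46 and 2.75-fold, respectively". The accumulation rows assume 21-day dosing, because the protocol equates 6-9 weeks with 2-3 dosage cycles.

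| Basis | Calculation | Share at 28 days |
|---|---|---|
| Stated half-life | 2^(-28/27) | 49% |
| Clearance and volume | ln 2 x 6.9/0.20 = 23.9 d; 2^(-28/23.9) | 44% |
| AUC accumulation | (1 - 1/1.91)^(28/21) | 37% |
| Cmin accumulation | (1 - 1/2.75)^(28/21) | 55% |
| Cmax accumulation | (1 - 1/1.46)^(28/21) | 21% |
| Two-compartment, central volume assumed 2.5-5 L | fitted to 0.20 L/day, 6.9 L, 27 d | 21-35% of peak |

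In the two-compartment case D365 is at about 60% of the steady-state average. The 23.9 days against 27 is not an error in the protocol, because the steady-state volume is not the terminal-phase volume. In every row D365 is the usual 4-week trough.

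**4. If dosing was switched to every 2 weeks** (Protocol 9.3.2), the last infusion could fall on cycle 13 day 15, D351. The gap is then 14 days: 2^(-14/27) = 0.698, or about 70%.

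**5. How far the residual reaches into the 336-day period** (12 x 28), at a 27-day half-life from D337:

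| Share left | Days after infusion | Study day | Days into period | Share of 336 |
|---|---|---|---|---|
| 25% | 54 | D391 | 26 | 8% |
| 10% | 90 | D427 | 62 | 18% |
| 5% | 117 | D454 | 89 | 26% |
| 3.1% (5 half-lives) | 135 | D472 | 107 | 32% |

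Beyond D472, 336 - 107 = 229 days remain.

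**6. Effect on the tables.** A patient whose first event of a given type starts between D365 and D472 is counted in the later phase and not under the combination. For patients with at least one event, this can only lower or leave unchanged the combination proportion, and only raise or leave unchanged the later one. A patient who already had that event during the combination does not change the combination count. For events per person-time no direction follows: a carry-over segment adds both events and days, and the rate depends on how many events occur per day after D365, which the documents do not give.

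**The case against.** The strongest case against is that the analysis is descriptive and exploratory, no between-phase contrast is specified, and no AE is lost from the Safety Set. SAP 6.9 lists onset timing relative to dosing and five-level causality. Protocol 13.9.1 lists atezolizumab AESIs separately from those for bosutinib. Late immune-type events could therefore be found and re-sorted. That is true, but no planned table re-sorts them, and a window chosen after seeing the data would be post hoc. The AESIs named in the SAP are vascular events plus an investigator catch-all, not the protocol's atezolizumab list.

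Three stronger readings are tempting and are not supported:
- **That the protocol itself predicts new events after stopping.** Protocol 11.6.2 says "Discontinuation of atezolizumab may not have an immediate therapeutic effect". In context this explains why severe toxicity already present may need acute treatment. It concerns slow resolution, not new onset. The step from residual drug to new events is an inference from the half-life.
- **That the SAP reports these events as toxicity of bosutinib alone.** It uses no such label. It lists four phases for a design with three therapies. The FAS definition in SAP 6.2 places the combination within the first three phases, which makes the later monotherapy the fourth. Protocol 11.5 calls it the third treatment phase. On either reading a subset opens when infusions end, but the mapping is unsettled.
- **That the bias has one direction.** This holds for cumulative patient proportions only. A longer exposed window also cannot lower cumulative incidence, simply because it is longer.

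The objection to a fixed 135-day exposed period also stands in part. Five half-lives is a convention that appears in neither document. AEs are collected routinely only to about 28 days after the last dose or the decision to stop (Protocol 12.21 and 13.4; SAP 6.9), so a patient withdrawn during the combination cannot supply 135 days.

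**Conclusion.** The point holds as a gap in attribution for the primary objective. The post-combination subset opens at an ordinary atezolizumab trough: about 49% of the post-dose level on the stated half-life, roughly 20-55% across derivations, and about 70% if the last infusion was at D351. By the five-half-life convention, up to 107 of its 336 days (32%) carry residual drug.

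This rests on nominal visit days, allocation by AE onset date (the natural reading, not a stated rule), and the protocol's pharmacokinetic figures. How many AEs are affected cannot be computed from the documents. They do not support replacing the primary reporting periods with a fixed 135-day exposed window. They do support a supplementary split, which is a cheap improvement.

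**What to change.** In SAP 6.5 and 6.9, with matching text in Protocol 15.3.1:

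1. Reconcile the four phases with the three therapies, and state that an AE is allocated by date of onset or worsening.
2. Keep the phase table. Within the post-combination period, add a split by time since the last actual atezolizumab infusion. Show a pre-specified carry-over segment as its own column (for example up to 5 x 27 = 135 days, about D365 to D472, labelled as a convention) and the remainder as bosutinib only. Using actual infusion dates also covers patients who missed up to three infusions (Protocol 11.6).
3. Report rates per person-time beside the percentages. State that patients withdrawn during the combination contribute only about 28 days after their last dose.

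The cost is SAP wording, a matching protocol edit and one variable derived from infusion and AE onset dates. Treatment and visits do not change, and the calendar-phase table stays recoverable. The downsides are a shorter bosutinib-only period (about 229 days instead of 336), some true bosutinib events in the carry-over column, and unequal follow-up for withdrawn patients.

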13.8 SAEs

The definitions and reporting requirements of ICH Guidelines for Clinical Safety Data Management, Definitions and Standards for Expedited Reporting, Topic E2A, as well as the Royal Decree 1090/2015, of 4 December, regulating clinical trials with medicinal products, Ethics Committees for Investigation with medicinal products and the Spanish Clinical Studies Registry will be followed.

The investigator or sponsor may determine the seriousness of an AE based on the following. An AE is considered a SAE if at least one of these conditions applies:

- *Death:* if the death occurs within the time of the first dose and the 28 days after the last dose and the cause of death is the event.
- *Life-threatening:* An AE that places the patient, in the view of the investigator or the sponsor, at immediate risk of death from the event as it occurred (e.g., this does not include an event that, had it occurred in a more severe form, might have caused death)
- Results in a persistent or significant incapacity or substantial disruption of the ability to conduct normal life functions
- *Inpatient hospitalization or prolongation of existing hospitalization:* Hospitalization refers to admission of a patient into a hospital for any length of time.
- *A congenital anomaly/birth defect:* A fixed, permanent impairment established at or before birth

- Is a significant medical event in the investigator's judgment (e.g., may jeopardize the patient or may require medical/surgical intervention to prevent one of the outcomes listed above)

Events that are clearly consistent with the expected pattern of progression of the underlying disease should not be recorded as serious adverse events SAES.

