15.3.2 Adverse Events

Summary tables for adverse events (AEs) have to include only AEs that started or worsened during the on-treatment period, the treatment-emergent AEs (TEAEs). However, all safety data (including those from the pre-treatment period) will be listed and those collected during the pre-treatment period are to be flagged.

The incidence of treatment-emergent adverse events (new or worsening from baseline) will be summarized by system organ class and/or preferred term, severity (based on CTCAE grades), type of adverse event, causality relation to study treatment by the phases or subsets previously described.

Deaths reportable as SAEs and non-fatal serious adverse events will be listed by patient and tabulated by type of adverse event and safety subset.

Specific safety event categories will be considered. Such categories consist of one or more well-defined safety events which are similar in nature and for which there is a specific clinical interest in connection with the study treatment(s).

For each specified safety event category, number and percentage of patients with at least one event part of the safety set will be reported. Also AESI will be summarized and analyzed.

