6.4. Outcome definitions

The primary objective is to evaluate the safety profile of bosutinib 400 mg daily in combination with atezolizumab as first line treatments in participants with chronic myeloid leukemia. The safety set population will be used for all safety analyses. For a detailed description of safety variables analysis see the 6.9 Safety Data Analysis section.

➤ Secondary variables:

- Major Molecular Response (MMR) and Molecular Response (MR) rates at 3, 6, 12 months and at the End of Treatment (EoT) visit.
- Percentage of participants alive at months 6 and 12 and at the EoT visit.
- Number of confirmed MR4 and MR4.5 at end of treatment.
- The rate of confirmed MR4 and MR4.5 at the end of treatment.
- Number of Complete Cytogenetic Responses (CCyR) at 1 year]
- The rate of Complete Cytogenetic Response (CCyR) at 1 year.
- Number of days to response (CCyR, MMR, MR4, MR4.5). [Time Frame: at the EoT visit]
- The median time to response and the overall estimated probability of response (CCyR, MMR, MR4, MR4.5).
- Number of overall surviving patients [Time Frame: at the EoT visit]
- Number of progression-free survival patients.[Time Frame: at the EoT visit]
- Number of failure-free survival patients. [Time Frame at the EoT visit]
- Number of event-free survival patients. [Time Frame: at the EoT visit]
- Immunological Studies: phenotypic Assays:
 - Cell characterization: NK cells (CD3- CD56+; CD16+ CD56+; TNF α ; IFN α ; Granzyme b NK-LGL cells (CD56+ CD57+), T-LGL cells (CD3+ CD57+), CD8 TCR α/β , NK markers (NKG2D, KIR2DL2/DL3/DS2, KIR2DL5B).
 - b. Differentiation and maturation (NKG2A/CD16) and proliferation (NK67) markers of NK cells.

- c. CD4+ T cells activation markers: CD25 CD69 HLA-DR.
- d. Predictive markers of CML relapse: T regs (CD4+ CD25int-hi CD127low), CD8+ T cells (PD-1/PD-L1) and plasmacytoid dendritic cells (CD86+).

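### The only death table named in the safety analysis covers SAE-reportable deaths, so the tabulated count can fall below the number of deaths known in the safety set

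*SAP*

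**What the plan says.** The adverse-event part of SAP 6.9 plans one output for deaths: "Deaths reportable as SAEs and non-fatal serious adverse events will be listed by patient and tabulated", broken down by event type and by study-phase subset. Protocol 15.3.2 has the same sentence ("Deaths reportable as SAEs and non-fatal serious adverse events will be listed by patient"). Neither section names a table of deaths from all causes.

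Protocol 13.8 decides which deaths qualify:

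- The death criterion applies "if the death occurs within the time of the first dose and the 28 days after the last dose", and the event must also be the cause of death.
- Progression is carved out: "Events that are clearly consistent with the expected pattern of progression of the underlying disease should not be recorded as serious adverse events".
- The criteria are alternatives: "An AE is considered a SAE if at least one of these conditions applies".

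SAP 6.9 also has a general listing statement: "all safety data (including those from the pre-treatment period) will be listed".

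Deaths from any cause enter the plan elsewhere as secondary endpoints in SAP 6.4: the percentage alive at months 6 and 12 and at EoT, and "Number of overall surviving patients [Time Frame: at the EoT visit", together with progression-free, failure-free and event-free counts. Protocol 15.4.1 groups these under efficacy variables.

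**The concern.** Safety of the combination is the primary objective, and Protocol section 7 describes a disease in which life expectancy is now close to normal. In that setting the number of deaths, with their causes, is the first figure a reader looks for. As written, whether a known death reaches the safety table depends on two things: whether the investigator or sponsor judges it clearly a progression event, in an open-label trial, and how long after the last dose it occurred. A death left out for either reason would leave no trace in the table, and the reader would have no way to tell that the tabulated count was not the full count.

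**Working it through.** The documents give no expected number of deaths, so there is no planned death figure to reproduce. The one derived number nearby does reproduce: 36 × (1 − 0.15) = 30.6 patients entering the combination, against the 30-31 given in SAP 4.3 and Protocol 15.5.

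**Step 1. Which deaths the safety table takes in.** Protocol section 4 counts CML-related death as disease progression. Protocol 13.8 keeps events that are clearly progression out of the SAEs. A clear CML death is therefore not SAE-reportable and is not in the table. Separately, the death criterion ends 28 days after the last dose, and the closing line of SAP 6.9 uses the same 28-day recording window.

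**Step 2. Who can die outside the 28-day window and still be known.** For completers, 25 cycles × 28 days = 700, so EoT is D700. The EOS visit is at 700 + 28 = D728, the last scheduled contact (Protocol Tables 15 and 17), so no planned visit would find a later death. The gap mainly concerns early withdrawals. Protocol 11.6 withdraws patients who miss atezolizumab four or more times or are off bosutinib for more than a month. Protocol section 4 (premature withdrawal) keeps survival monitoring open for them, without a schedule.

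**Step 3. Whether the survival endpoints cover the same deaths.** No analysis set is assigned to them. SAP 6.4 assigns the Safety Set to safety analyses only. Protocol 11.6 links the efficacy analysis to the PPS, which lies inside the FAS. Both wordings of the FAS (Protocol section 4; Protocol 15.1.1 and SAP 6.2) require completion of the combination.

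| Death | SAE death table | Survival endpoints |
|---|---|---|
| Fatal AE, not progression, within 28 days of last dose | In | In if all treated patients are used and it falls by EoT |
| Clear CML death before the 12 combination cycles are complete | Out | In if all treated are used; out if FAS or PPS |
| Clear CML death during the third therapy | Out | In, but with no cause shown (PPS: only if compliant) |
| Later than 28 days, outcome of a reported SAE | The event is already in the SAE output under another criterion | Depends on the set and the EoT time frame |
| Later than 28 days, early withdrawal, no prior reported SAE | Not assured | Depends on the set and the EoT time frame |

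On the FAS or PPS reading, the second row is absent from both outputs.

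**Step 4. Size of one omitted death.** Exact binomial intervals, the method in SAP 6.5, with n = 36 and assumed counts:

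- 0 deaths: 0%; upper limit 1 − 0.025^(1/36) = 9.7%.
- 1 death: 1/36 = 2.8%; lower limit 1 − 0.975^(1/36) = 0.07%, shown as 0.1%; the upper limit solves P(X ≤ 1) = 0.025 and is 14.5%.
- 2 deaths: 2/36 = 5.6% (0.7 to 18.7%).

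With 31 patients in the combination period, the step from 0 to 1 death is from 0% (0 to 11.2%) to 3.2% (0.1 to 16.7%).

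**The case against.** The case against has real force on four points.

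- **Listing.** A reader might infer that excluded deaths are not even listed. The documents do not support that, because SAP 6.9 lists all safety data. But a general listing is not a count, and the plan does not say whether a progression death recorded only on the end-of-treatment form counts as safety data.
- **Late fatal events.** A reader might infer that a late immune-related death can never reach the safety tables. That is too strong. The SAE criteria are alternatives, so such an event can qualify as life-threatening or through hospitalization. Ongoing SAEs are followed past day 28 (Protocol 12.21), and SAEs arising after participation ends are reported if the investigator learns of them (Protocol 13.4). What remains is a death with no prior reported SAE, found only if someone hears of it.
- **Survival endpoints.** OS has no restriction by cause, PFS counts any death, SAP 6.5 applies Kaplan-Meier to all time-to-event endpoints, and CML death is collected at end of treatment (Protocol 12.20). So a progression death is not necessarily lost to the report. This back-up is sound only if the endpoints use all treated patients, which neither document states, and even then it gives no cause and ends at EoT.
- **Data source.** Protocol 12.20 describes a visit within 14 days of stopping and cannot supply late deaths. That stands, and it limits the remedy to deaths already known.

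The role of judgement should not be overstated either: the sponsor may also determine seriousness, and the carve-out covers only clear progression.

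**Conclusion.** The point holds as a reporting gap. Following SAP 6.9 and Protocol 15.3.2 as written, the tabulated death count can be lower than the number of deaths known in the safety set. This is certain for a death recorded as clear CML progression, and possible for a death beyond 28 days with no earlier SAE report. One such death in 36 moves the tabulated rate from 2.8% to 0% and its exact upper limit from 14.5% to 9.7%.

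This assumes that all 36 patients are dosed. The death counts are illustrations, and the documents give no basis for a probability that an omission will occur. That the survival endpoints might be run in completers only is an inference from the efficacy label and Protocol 11.6; no text says so, and none rules it out. The documents do not support the further conclusion that progression deaths or late deaths are absent from the whole report.

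**What to change.** 1. In SAP 6.9 and Protocol 15.3.2, replace the restriction to SAE-reportable deaths with: all deaths known in the Safety Set from first dose to the data cutoff (the last patient's last visit, per the synopsis), listed by patient and tabulated by cause (treatment-related, CML progression, other), therapy period and days since the last dose of each drug. Show SAE-reportable deaths as a subset of that table and leave non-fatal SAEs as planned.
2. In SAP 6.4 or 6.5, state that the survival endpoints are analysed in all treated patients.

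No new follow-up is required; deaths after a patient's last contact are included only if they are known. The cost is one extra table with its listing and a reported death count that may be slightly higher.
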